2.2 Continuous Glucose Monitor (CGM) device

The commercially available Dexcom G6 CGM system (Figure 3) measures the glucose level in the interstitial fluid under the skin. The CGM system includes a sensor which has a small wire that is inserted under the skin, a transmitter that attaches to the sensor and a smartphone app that collects and displays the glucose results. The sensor will be placed under the skin and can stay in place for up to 10 days. The sensor will measure the glucose level in the interstitial fluid every five minutes and transmit that data to the smartphone. The screen will show in real-time the participant’s glucose value, most recent glucose trends, and an arrow indicating which way the glucose trend is predicted to go. Alarms can

be set to alert the participant to glucoses that are too high or too low, or if glucose trends are changing quickly. The data collected by the system can be downloaded and evaluated for several CGM-based metrics.

Figure 3: Dexcom G6 CGM System

3 Objectives

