5.4 CGM Device and Training

CGM device and smartphone app training will occur at the start of both treatment periods, and user guide materials will be provided. Participants will first download the Dexcom G6 Mobile app to their smartphone. After entering their transmitter's serial number into the app, there is a 2 hour warm-up for the CGM. Next they will identify a location on their abdomen as directed by study staff for insertion of the sensor. After cleaning the skin, participants are instructed how to use the applicator to insert the sensor and connect the transmitter to the sensor. After the 2 hour warm up is over, the CGM will start transmitting real-time glucose data. Participants will be allowed to use CGM data for their diabetes management. Blood glucose monitoring can be performed using the participant's own glucose meters if CGM readings do not match a participant's symptoms. CGM alert thresholds will be set at default levels of 70 mg/dL for low glucose, and 180 mg/dL for high glucose. These alerts can be adjusted during the study as needed. The G6 app also has a feature where wearers can mark events such as food or exercise; for the purposes of this study, participants will be instructed to use the "other" activity as a marker of symptomatic hypoglycemia (which they can use as an alternative to the hard-copy participant journal for documentation of symptomatic hypoglycemia)

[figure not shown]

Figure 13: Inserting the CGM Sensor

The Dexcom G6 system allows for the wearer to share their glucose data with up to 5 followers remotely through the Follow app. This "sharing" feature will be downloaded and started with assistance of the study staff. The study staff, including the PI, will have 24 hour access to this data for safety purposes, if participants call with any concerns during the study. A CLARITY mobile account will be set up for participants (using the CLARITY app which links to the G6 Mobile app) and linked to the research site, which can capture device data for analysis.

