7.1.3 Phone Visit 3: Safety Check (visit 2 +1 day)

The following procedures will be performed at this visit:

- Study staff phone call to assess IN insulin compliance and AEs/SAEs
- Reinforce SipNose device training
- Reinforce daily diary training
- Review CGM data in Clarity

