7.1.5 Visit 5: End of Treatment Period 1 (Day 17 +/- 3 days)

The following procedures will be performed at this visit:

- Safety check and assess AEs/SAEs
- Gold score (for data collection purposes only)
- Medication review for any changes since screening
- VS (blood pressure/pulse)
- MNSI survey
- Hypo surveys
- Document BG values before and after cognitive testing
- Cognitive tests (study drug must have been taken prior to testing)
- Review daily diary
- Evaluate CGM for adequate data collected
- Inventory returned devices
- Download SMBG for safety, if used
- Download and review CGM data
- Provider to see patient at this visit for visit assessment review
- In the event the study site is recommending no non-essential in person clinic contacts (such as during the COVID-19 pandemic), this visit may be done remotely and study staff will obtain as much of the above procedural information as possible. Procedures such as MNSI survey and VS may not be able to be done.

7.1.6 Phone Visit 6: Safety Check 1 Week into the 2 Week Washout (Day 24 +/-2 days)

The following procedures will be performed at this visit:

- Study staff phone call to assess for AEs/SEs

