7.1.7 Visit 7: Crossover/Start of Period Treatment 2 (Day 31 +/- 2 days)

The following procedures will be performed at this visit:

- Safety check and assess AEs/SAEs
- Medication review for any changes since screening

- Vital signs (blood pressure/pulse)

Administer first dose of intranasal insulin in clinic after above testing done, observe patient for 4 hours (only if randomized to intranasal insulin for treatment period 2).

The following procedures will be performed after the first dose is administered:

- SipNose device teaching
- Teach daily diary (or how to document within the G6 app that symptomatic hypoglycemia is commencing)
- Teach glucagon and hypoglycemia management
- Download SMBG for safety (if used)
- CGM placed
- Teach CGM & apps (Including G6, Clarity, Follow apps); provide user guide materials
- Provider to see patient at this visit for visit assessment review
- Subject instructed to call if any hypoglycemia before phone call occurs the next day
- In the event the study site is recommending no non-essential in person clinic contacts (such as during the COVID-19 pandemic), this visit may be done remotely and study staff will obtain as much of the above procedural information as possible, IF the participant is beginning the saline phase of the study only (not for insulin start). Distribution of supplies may be done remotely as well. If the participant is to begin the intranasal insulin part of the study, then the washout will be extended until a time when non-essential clinic visits at the site are permitted.

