12.1 Analysis Overview

Discrete variables will be summarized using frequencies and percentages, while continuous variables will be summarized by mean and standard deviation or median and interquartile range, as appropriate. Baseline variables will be compared between groups to ensure randomization achieved a balanced design. Distribution of the outcome variables will be assessed to determine if the planned analyses are appropriate. All analyses will be performed on an intention-to-treat basis. Missing data will be considered to be missing at random and those subjects will be excluded from analysis. If a large proportion of data is missing (>10%), we will compare baseline characteristics between subjects with missing and non-missing data. No adjustment for multiple comparisons will be done. All statistical analyses will be performed in SAS Version 9.4.

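### The exclusion rule for missing data turns a declared intention-to-treat analysis into a complete-case one. If lows on insulin cause the loss, the primary result leans towards non-inferiority, and no planned analysis would show it.

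*Combined protocol and SAP*

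**What the plan says.** Section 12.1 first says "All analyses will be performed on an intention-to-treat basis". The next sentence is "Missing data will be considered to be missing at random and those subjects will be excluded from analysis". The only further step is "If a large proportion of data is missing (>10%), we will compare baseline characteristics between subjects with missing and non-missing data". Section 12.2 adds a least squares model with a two-sided 95% confidence interval and a 2-point margin. No sensitivity analysis for missing data appears in either section.

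Other sections show that CGM will often exist for people who leave:
- Section 5.4: each participant's account is set up "and linked to the research site, which can capture device data for analysis".
- Sections 7.1.3, 7.1.4, 7.1.8 and 7.1.9: each phone visit during treatment includes "Review CGM data in Clarity".
- Section 5.6: participants who stop treatment continue follow-up as far as possible.

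Sections 7.1.5 and 7.1.10 require staff to "Evaluate CGM for adequate data collected", without saying what is adequate. Section 10.3 allows withdrawal for clinically significant adverse events or intolerance of study medication, and requires the reason to be documented.

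**The concern.** Excluding every participant with missing data is a complete-case analysis. Missing at random allows loss to depend on values already observed, for example lows already recorded on insulin. Under that kind of loss the completers are a selected group, and their mean difference is biased. A likelihood analysis of all recorded periods uses the assumption properly; deleting the participants does not.

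The clearest case is an insulin-first participant who leaves because of lows and never starts placebo. The insulin period is on record, and the rule removes it. The endpoint is time below 54 mg/dL, so the analysis would lose the kind of participant in whom the harm would appear. In a safety trial that is the wrong direction for an error.

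The planned check does not help. A baseline comparison cannot detect loss that arises from lows during the study. Counted in participants, 1 lost of 10 is exactly 10% and does not exceed the trigger.

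**Working it through.** **Convention.** Difference = insulin minus placebo in percentage points; non-inferior if the upper 95% limit is below 2. This mirrors section 12.2, which uses the opposite sign and a lower limit of -2.

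**Inputs from section 12.4.** 10 participants, 5 per sequence; within-subject SD (root mean square error) 1.4; margin 2; true difference 0 for power.

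**The plan's own figure.** SE = 1.4 × √(½ × (1/5 + 1/5)) = 0.626. With 8 df, t = 2.306; noncentrality = 2/0.626 = 3.194. Power = 79.84%, against 79.8% stated. If loss is unrelated to outcome, power falls to 73.4% with 9 analysed (5+4) and 66.5% with 8 (4+4), and the error rate stays near 2.5%.

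**Bias if high insulin values cause loss (illustration).** The documents give no dropout rate and no between-subject SD. Assumptions: normal data, between-subject SD 0.7 to 2.8, true difference +2, 10 randomised, participants in the top 10%, 20% or 30% of insulin-period values lost, at least 2 completers per sequence. 200,000 simulated trials per case. False non-inferiority under complete-case analysis:

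| Between-subject SD | Insulin-first only lost (10/20/30%) | Both sequences dropped (10/20/30%) |
|---|---|---|
| 0.7 | 3.6 / 4.5 / 5.6% | 5.0 / 7.9 / 11.1% |
| 1.4 | 3.3 / 4.0 / 4.8% | 4.3 / 6.2 / 8.1% |
| 2.8 | 2.9 / 3.4 / 3.9% | 3.6 / 4.6 / 5.4% |

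The mean estimate falls from 2 to 1.69-1.94 (first column of results) or 1.38-1.88 (second). The second column requires placebo-first participants with a shortened insulin period to be dropped as well, which section 12.1 does not settle.

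**Tipping point, 10 randomised.** Let the completers average 0 with SD of differences 1.4 × √2 = 1.98 (variance 3.92). The upper limit is t × 1.98 × √(1/n₁ + 1/n₂)/2:
- 9 completers (4+5): 2.365 × 0.664 = 1.57.
- 8 completers (4+4): 2.447 × 0.700 = 1.71. With 3+5: 2.447 × 0.723 = 1.77.

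Now restore the excluded participants at difference x each, so that the analysis is 5+5 with 8 df, and re-estimate the variance. The SE is √(SS/8) × 0.316.
- One participant: estimate x/10; SS = 7 × 3.92 + 0.8x². At x = 3.84: 0.384 + 2.306 × 0.701 = 2.00.
- Two, one per sequence: estimate x/5; SS = 6 × 3.92 + 1.6x². At x = 2.52: 0.504 + 2.306 × 0.649 = 2.00.
- Two, both insulin-first (from 3+5): estimate x/5; SS = 6 × 3.92 + 1.2x². At x = 2.69: 0.537 + 2.306 × 0.634 = 2.00. If instead 4+4 completers remain and the restored set is 6+4, the value is about +2.8.

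One point is 14.4 minutes a day, so +3.84 is about 55 minutes a day.

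**Why a minimum wear is needed.** Section 2.2: "The sensor will measure the glucose level in the interstitial fluid every five minutes and transmit that data to the smartphone". That is 288 readings a day. One 30-minute low (6 readings) is 6/288 = 2.08% of a single day, more than the margin, but 6/4,896 = 0.12% of 17 days.

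**The case against.** **The mechanism is assumed.** Participants may act on real-time CGM with an alert at 70 mg/dL (section 5.4), and non-severe hypoglycemia is not an adverse event (section 11.6.1). Losing everyone above a cut-off is an extreme model, and normality is a rough fit to a percentage bounded at 0. This stands: the error rates are illustrations, not forecasts.

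**The contradiction may be softer than it looks.** Intention-to-treat may mean only analysis by assigned sequence, and a shortened period might be kept as adequate. A reader might infer that the plan certainly discards all partial CGM. The documents do not support that, because neither missing nor adequate is defined. What remains firm is the participant with no second period at all.

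**The large figures depend on the unsettled reading.** A reader might take 11% as the trial's error rate. That needs partial insulin periods in both sequences to be dropped, 30% loss and the smallest between-subject SD. The firmer case is about 3-5.6%, which is modest.

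**The tipping values are not discarded records.** A reader might infer that the rule throws away observed differences of +2.5 to +3.8. For an insulin-first participant who never reached placebo no difference exists; it has to be imputed.

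**Not all loss is harmful.** When in-person visits are suspended and insulin is the next treatment, section 7.1.7 says "then the washout will be extended until a time when non-essential clinic visits at the site are permitted". A placebo-first participant lost through that delay costs power only.

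None of this repairs the rule. Enrolling until 10 complete would protect power, but the analysis set would still be completers.

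**Conclusion.** The concern holds, in conditional form. Section 12.1 prescribes complete-case analysis under an intention-to-treat label, and missing at random does not in general justify it. The bias runs towards non-inferiority only if lows on insulin cause the loss. Under the assumptions above, false non-inferiority is then about 3-5.6% instead of 2.5%, and up to about 11% only on the reading that the plan leaves open. With so few participants, one or two exclusions could decide the conclusion, and the reported interval would not reveal it. The sponsor should change this. It is not a fatal flaw: the documents do not show that such loss will occur, and the effect on the firmer reading is modest.

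**What to change.** Replace the exclusion sentence in section 12.1 with:

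*Every randomised participant with usable CGM in at least one treatment period is included in the primary analysis, a mixed model with treatment, period and sequence as fixed effects, subject as random effect, and Kenward-Roger degrees of freedom. The minimum CGM wear for a usable period is [stated number of hours or days], fixed before any CGM outcome data are reviewed.*

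Then:
- Name all recorded CGM in the assigned period as the primary analysis, consistent with intention-to-treat.
- Name the on-drug analysis (CGM up to the last dose in the period) as a sensitivity analysis, and say so plainly if the two disagree. Off-drug CGM can dilute the difference. If 10-30% stop for unrelated reasons after 30-50% of the period, with no effect afterwards, a true difference of 2 shrinks to between 2 × (1 - 0.30 × 0.70) = 1.58 and 2 × (1 - 0.10 × 0.50) = 1.90.
- List periods below the minimum with their wear and observed value.
- Add one tipping-point analysis that moves missing or unusable values against insulin until the non-inferiority conclusion changes, and report that value.

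**Cost.** SAP wording and a few runs in the SAS version already named; no new data collection. Partial periods are noisier, so power is slightly lower. The mixed model still relies on missing at random and removes only part of the bias. Its simulated false non-inferiority of 2.7-4.2% assumes that every leaver's insulin value is kept, so it does not describe the rule once a minimum wear applies. The tipping-point analysis covers that gap.

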12.2 Statistical Analysis of Primary Outcomes

The primary objective of this study is to assess non-inferiority of dangerous hypoglycemia with administration of intranasal insulin in T1D participants with intact awareness of hypoglycemia. A two-sided 95% confidence interval will be reported for the difference between the two treatment periods based on a least squares model. A non-inferiority margin

[figure not shown]

Figure 14: Possible outcomes of non-inferiority analysis

of 2% (approximately 30 minutes per day) will be used (see Section 12.4 for justification). The null hypothesis of inequality (difference is greater than or equal to 2%) is rejected in favor of the alternative hypothesis of equality (difference is less than margin) if the lower limit of the confidence interval is greater than -2%.

Since non-inferiority is typically framed in terms of a one-sided test, it is worth noting that the left half of a two-sided test at $\alpha = 0.05$ gives the same rejection region as a one-sided test at $\alpha = 0.025$. Therefore, reporting a two-sided 95% confidence interval will provide flexibility to test for inferiority if non-inferiority cannot be declared while maintaining the overall type 1 error rate at 5%. Figure 14 shows the inference to be drawn for various scenarios of the two-sided 95% confidence interval.

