7.1.10 Visit 10: End of Treatment Period 2 (Day 48 +/- 3 days)

The following procedures will be performed at this visit:

- Safety check and assess AEs/SAEs
- Gold score
- Medication review for any changes since screening
- VS (blood pressure/pulse)
- Height/weight/BMI
- MNSI survey
- Hypo surveys (Clarke, HypoAQ)
- Document BG values before and after cognitive testing
- Cognitive tests (study drug must have been taken prior to testing) (RBANS, Trail-making)
- Smell test (12-item UPSIT test versions A & B)
- Review daily diary
- Download SMBG for safety (if used)
- Evaluate CGM for adequate data collected

- Inventory returned devices
- Review CGM data in Clarity
- Provider to see patient at this visit for visit assessment review
- In the event the study site is recommending no non-essential in person clinic contacts (such as during the COVID-19 pandemic), this visit may be done remotely and study staff will obtain as much of the above procedural information as possible. MSNI, VS, height/weight/BMI may not be able to be obtained. Supplies may need to be returned remotely.
- Study visits 10 and 11 may be combined into 1 visit to conclude the patient's participation in the study, with as many of the data points for both of these visits being obtained at the same visit. Any assessments that are able to be done remotely (such as assessment of AE/SAEs) may be done remotely by phone.

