12.4 Power Calculation

The study is powered on our primary objective of determining non-inferiority of dangerous hypoglycemia with administration of intranasal insulin in T1D participants with intact awareness of hypoglycemia. The non-inferiority margin of 2% is based solely on clinical judgement. A total sample size of 10 (5 per sequence arm) achieves 79.8% power to detect non-inferiority assuming a true mean difference of 0 and a square root of within mean square error of 1.4%. This power calculation was conducted using the PASS v16 module for non-inferiority test for the difference between two means in a 2x2 cross-over design.

13 Study Conduct Considerations

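### Section 12.2 states the primary contrast as a difference between treatment periods, without a treatment contrast, a direction or the crossover model terms behind the 79.8% power

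*Combined protocol and SAP*

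**What the plan says.** Section 12.2 is the only place where the primary analysis is defined. It calls for a two-sided 95% confidence interval "for the difference between the two treatment periods based on a least squares model". The section names no treatment, period, sequence or subject term. It puts the null at a difference of 2% or more, yet rejects it when the lower confidence limit lies above -2%. It adds that the two-sided interval "gives the same rejection region as a one-sided test at $\alpha = 0.025".

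Section 12.4 gives the design inputs. The 2% margin rests on clinical judgement alone. On size and power it says: "A total sample size of 10 (5 per sequence arm) achieves 79.8% power to detect non-inferiority". The inputs to that figure are a true difference of 0 and a root within-subject mean square error of 1.4%. The figure comes from the PASS "module for non-inferiority test for the difference between two means in a 2x2 cross-over design".

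In the visit schedule, treatment period is a calendar term: "Visit 5: End of Treatment Period 1 (Day 17 +/- 3 days") and "Visit 10: End of Treatment Period 2 (Day 48 +/- 3 days"). Sections 7.1.2 and 7.1.7 provide for insulin to be started in either period, depending on the randomized sequence.

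**The concern.** If the words of 12.2 carry the meaning they have in the visit schedule, the interval compares Period 2 with Period 1. Both drugs are used in each period, so the contrast measures drift over time rather than the effect of insulin. This is the trial's only inferential question, and it concerns safety.

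If the words are taken to mean each participant's insulin period and saline period, two gaps remain. First, a least squares model could be a full crossover analysis, a paired comparison that ignores period, or a comparison that ignores the pairing. With 10 participants these can differ in power. Second, the order of subtraction is not stated in the text, and the null and the rejection rule fit opposite orders. Figure 14 may show the direction, but it is not reproduced in the copy reviewed.

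**Working it through.** **Inputs.** From 12.2 and 12.4: N = 10, 5 per sequence; margin 2 points; true difference 0; within-subject SD 1.4; one-sided alpha 0.025. The documents give no period effect and no between-subject SD, so both are varied below as assumptions. Simulations use normal data.

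**1. The stated power.** For a 2x2 crossover, SE = 1.4 x sqrt(2/10) = 0.626 and the noncentrality is 2/0.626 = 3.194. There are 20 observations. Ten subject parameters (which absorb the intercept and sequence), one for period and one for treatment leave 20 - 12 = 8 error df. The noncentral t with 8 df gives 0.7984, which is the stated 79.8%. The figure is correct and belongs to a model with subject, period and treatment terms.

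**2. The literal period contrast.** Let pi be the period effect (Period 2 minus Period 1) and tau the insulin effect.
- Insulin first: the expected Period 2 minus Period 1 difference is pi - tau.
- Saline first: it is pi + tau.
- Averaged over n1 insulin-first and n2 saline-first participants: pi + tau x (n2 - n1)/N.

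At 5/5 this equals pi, and tau drops out. At 6/4 or 4/6 only -0.2 tau or +0.2 tau remains. Unequal completers are possible, because 12.1 excludes participants with missing data.

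Take tau = 2 and pi = 0 at 5/5. The estimate has mean 0. The paired differences have variance 2 x 1.96 = 3.92 from error, plus 10 x 4/9 = 4.44 because the two sequences are shifted by -2 and +2. The estimated SE is therefore about sqrt(8.36/10) = 0.914, and the half-width is about 2.262 x 0.914 = 2.07. The simulated rate of declaring non-inferiority is about 49%. For the crossover treatment contrast it is 2.5%, as it should be at the margin.

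**3. Treatment contrast with terms left out (true difference 0).**

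| Model | Assumption | Power |
|---|---|---|
| Subject, period, treatment (8 df) | any period effect or between-subject SD | 79.8% |
| Subject, treatment (9 df) | no period effect | 81.1% |
| Subject, treatment | period effect 0.5 | about 79% |
| Subject, treatment | period effect 1 | about 73% |
| Subject, treatment | period effect 1.5 | about 63% |
| Subject, treatment | period effect 2 | about 49% |
| Treatment only, no period effect | within-subject correlation 0 | about 86% |
| Treatment only, no period effect | correlation 0.2 | about 79% |
| Treatment only, no period effect | correlation 0.5 (between-subject SD 1.4) | about 60% |
| Treatment only, no period effect | correlation 0.7 | about 33% |
| Treatment only, no period effect | correlation 0.8 (between-subject SD 2.8) | about 16% |

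The correlation is SB²/(SB² + 1.96), where SB is the between-subject SD. For example, 1.96/(1.96 + 1.96) = 0.5.

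**4. Direction.** Suppose the contrast is insulin minus saline, so that harm is positive, and the present rule is kept (lower limit above -2). At a true harm of 2 points the noncentrality is (2 + 2)/0.626 = 6.39. With 8 df the rule declares non-inferiority 99.98% of the time. It works only for saline minus insulin, whereas the stated null of a difference of 2% or more fits insulin minus saline.

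**The case against.** The strongest reply is that nobody would run the literal contrast. The sentence before the one at issue sets the aim as non-inferiority with intranasal insulin, and a margin and a possible test of inferiority make sense only for insulin against saline. Section 12.4 powers the same objective as a difference between two means in a crossover, with a within-subject error. The phrase in 12.2 carries no period numbers, and each participant has one insulin and one saline period. This stands as evidence of intent. A reader might infer from the wording that the wrong contrast will be run, and the documents do not support that. The 49% therefore describes the literal reading only and is not a property of the trial as probably intended.

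A reader might also infer that any model without subject or period terms falls below 79.8%. That is not so. Dropping period alone gives 81.1% when there is no period effect, and dropping both gives about 86% at correlation 0. The losses depend on quantities that the plan does not give, and a 2-point period effect is as large as the whole margin. Section 5.4 provides CGM training and real-time CGM in both periods, which tends to even them out. On the other side, participants may act on CGM readings, section 1.1 says that CGM can reduce hypoglycemia, and the meter-and/or-CGM download in 7.1.1 leaves room for participants new to CGM. Some drift between periods is plausible, but its size is unknown.

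The reply does not supply the missing model terms or settle the order of subtraction in the text.

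**Conclusion.** The point holds as a fault of specification. Section 12.2 uses a phrase that, in the protocol's own vocabulary, names a contrast in which the insulin effect cancels at 5 per sequence. It also leaves out the treatment contrast, its direction in the text, and the model terms on which 79.8% depends. The 79.8% itself is right.

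The 49% against 2.5% rests on the literal reading, equal sequences, no period effect, normal data and the plan's SD of 1.4. The power shortfalls are conditional on assumed period effects and within-subject correlations. The conflict between the null and the rejection rule needs no assumption beyond the visible text. It matters most if the contrast is clarified and the rule is left as it is. The text should be corrected before the analysis.

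**What to change.** In 12.2, replace the description of the contrast and model with:

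> The insulin-minus-saline difference in percent time <54 mg/dL from a linear model with sequence, subject within sequence, period and treatment.

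Replace the decision rule with:

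> Non-inferiority is concluded if the upper limit of the two-sided 95% confidence interval is less than +2%.

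The two edits must be made together, because the first without the second gives the 99.98% rate shown above. Check that Figure 14 uses the same direction.

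The cost is a small text edit. Compared with a paired analysis that ignores period, the model spends 1 error df (81.1% to 79.8% power when there is no period effect). In return, power no longer depends on the size of a period effect. Sample size and stated power are unchanged, since this is the model that 12.4 already assumes.

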3.1 Primary Objective

Demonstrate no significant increase in dangerous hypoglycemia with administration of intranasal insulin in T1D participants with intact awareness of hypoglycemia.

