4.1 Primary Endpoints

Dangerous hypoglycemia defined by percent time below range (<54 mg/dL) from real-time continuous glucose monitoring (CGM).

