12.3 Statistical Analysis of Secondary and Exploratory Outcomes

The secondary and exploratory objectives are purely descriptive. No inferential statistics will be performed. All measures of overall glycemic control, hypoglycemia awareness, and safety endpoints will be reported using the appropriate summary statistics. Values will be reported from baseline and conclusion of each dosing period.

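### Section 12.2 states the primary null hypothesis and its confidence-interval rule with opposite signs, so one half of the non-inferiority test is wrong whichever way the difference is taken

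*Combined protocol and SAP*

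**What the plan says.** - Section 3.1 gives the primary objective: "Demonstrate no significant increase in dangerous hypoglycemia with administration of intranasal insulin".
- Section 4.1 gives the endpoint: "Dangerous hypoglycemia defined by percent time below range (<54 mg/dL"), measured by continuous glucose monitoring. A higher value is worse.
- Section 12.2 says a two-sided 95% interval "will be reported for the difference between the two treatment periods based on a least squares model". The readable text does not say which treatment is subtracted from which.
- Section 12.2 sets the margin at 2%, without a sign, and states the hypothesis as "The null hypothesis of inequality (difference is greater than or equal to 2" percent). It rejects this in favor of the "alternative hypothesis of equality (difference is less than margin) if the lower limit of the confidence interval is greater than -2" percent.
- Section 12.2 adds that the same interval "will provide flexibility to test for inferiority if non-inferiority cannot be declared".
- Section 12.3, on the secondary and exploratory objectives: "No inferential statistics will be performed".
- Section 12.4 gives 79.8% power for 10 subjects, 5 per sequence, "assuming a true mean difference of 0 and a square root of within mean square error of 1.4" percent.

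Figure 14, which illustrates the possible conclusions, is not shown in the copy reviewed.

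**The concern.** A null of the form D >= +2 is rejected when the whole interval lies below +2, which is a condition on the upper limit. A lower limit above -2 rejects a different null, D <= -2. Section 12.2 pairs the first null with the second rule.

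This interval carries the trial's only planned inference on an outcome, and that inference concerns safety. The fallback test for inferiority uses the same interval, and everything else is descriptive. If the sign that fits the written null is combined with the written rule, the test protects against insulin lowering time below 54 mg/dL. It does not limit the chance of declaring non-inferiority when insulin raises it.

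**Working it through.** **1. Neither order of subtraction makes both halves right.** The harm is a higher value on insulin.

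| D defined as | Harm to exclude | Written null, D >= +2 | Written rule, lower limit > -2 |
|---|---|---|---|
| Insulin minus placebo | D >= +2 | Correct | Wrong: needs upper limit < +2 |
| Placebo minus insulin | D <= -2 | Wrong: describes insulin better by 2 points or more | Correct |

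**2. The plan's power figure.** Inputs from Sections 12.2 and 12.4: N = 10, root mean square error 1.4, margin 2, one-sided alpha 0.025, true difference 0.

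- SE = 1.4 x sqrt(2/10) = 0.626
- df = 10 - 2 = 8, so t(0.975, 8) = 2.306
- Planned 95% half-width = 2.306 x 0.626 = 1.44 points
- Power = P(noncentral t with 8 df and noncentrality 2/0.626 exceeds 2.306) = 79.84%

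This reproduces the stated 79.8%. At a true difference of 0 the lower-limit and upper-limit rules have equal probability by symmetry, so the power statement cannot show which sign was meant.

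**3. Chance of declaring non-inferiority.** Take D = insulin minus placebo, with true value d.

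- Written rule, lower limit > -2: noncentrality (d + 2)/0.626
- Aligned rule, upper limit < +2: noncentrality (2 - d)/0.626

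| True increase on insulin | Lower limit > -2 | Upper limit < +2 |
|---|---|---|
| 0 | 79.8% | 79.8% |
| 1 point | 98.6% | 29.1% |
| 2 points (the margin) | 99.98% | 2.5% |

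The right-hand column is also the written rule applied to placebo minus insulin, because a lower limit of (placebo minus insulin) above -2 is the same event as an upper limit of (insulin minus placebo) below +2.

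**4. How often the order of subtraction changes the written rule's answer.** Both columns were evaluated on the same data, with a normal estimate and the error variance integrated over chi-square with 8 df. Disagreement = P(lower rule) + P(upper rule) - 2 x P(both).

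- d = 0: both pass 60.78%, so 79.84 + 79.84 - 2 x 60.78 = 38.1% disagree; neither passes in 1.1%
- d = 1: both pass 28.04%, so 98.62 + 29.07 - 2 x 28.04 = 71.6% disagree
- d = 2: both pass 2.49%, so 99.98 + 2.50 - 2 x 2.49 = 97.5% disagree

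A simulation of 2,000,000 trials gave 38.1%, 71.6% and 97.5%.

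**5. One example.** Suppose insulin is observed 2 points higher with the planned half-width. As insulin minus placebo the interval is 2 - 1.44 = 0.56 to 2 + 1.44 = 3.44; its lower limit exceeds -2, so the written rule passes. As placebo minus insulin it is -3.44 to -0.56, and the written rule fails.

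**The case against.** The strongest reply is that the operative rule may be sound. The only explicitly signed number in the sentence is the -2% in the rule, and that rule is valid for placebo minus insulin. If the difference in the hypotheses is read loosely as the amount of worsening, the fault shrinks to a parenthesis. The two self-consistent versions (insulin minus placebo with the upper limit, placebo minus insulin with the lower limit) are mirror images and never disagree, so the 98.6% and 99.98% arise only if an analyst takes insulin minus placebo and still applies the lower-limit rule. Figure 14 may state the order. The full interval will be reported, and the DSMB (Section 13.2) reviews safety data, so an increase would be visible.

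Much of this stands. The large error rates are conditional on that combination; they are not a property of every reading of the plan. But the combination joins the sign implied by the written null to the rule as written, so it is a literal reading of the sentence. The rescuing reading needs one word to change meaning within the sentence, and the text does not say that it does. Figure 14 could show the intended sign but could not make both halves agree. The remark in Section 12.2 about the left half of a two-sided test does not settle it either: a left-tailed rejection of D >= 2 fits insulin minus placebo with the upper limit, which is not the limit named. A reported interval and safety oversight do not correct a wrong pre-specified conclusion.

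**Conclusion.** The concern holds. The mismatch follows from the text alone, with no assumption about the data, and it must be corrected because it defines success on the primary safety objective. The test can be applied, but the readable text allows two applications with different results. With placebo minus insulin, the written rule has the intended 2.5% error at a 2-point increase and only the null is misstated. With insulin minus placebo, the same rule declares non-inferiority in 99.98% of trials at that increase. The percentages assume the plan's 1.4% root mean square error, normal errors and 10 completers with 8 error degrees of freedom.

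**What to change.** In Section 12.2, define D as the insulin-versus-placebo treatment contrast from the 2x2 crossover model, replacing the reference to a difference between periods. Then use one of these equivalent forms:

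- D = insulin minus placebo; H0: D >= +2%; non-inferior only if the upper 95% limit is below +2%.
- D = placebo minus insulin; H0: D <= -2%; non-inferior only if the lower 95% limit is above -2%.

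State the inferiority rule on the same scale, and check that the axis and labels of Figure 14 match. The cost is a few words and one figure check. Sample size, margin, data collection and the 79.8% power stay as they are. The change should be made before outcome data are seen by treatment, so that the choice of sign cannot be questioned later.
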